1.0 PROTOCOL SUMMARY

Sponsor	Ablacon, Inc.
Study Name	FLOW EVAL-AF
Study Title	Electrographic flow mapping electrogram validation in patients with persistent atrial fibrillation
Clinical Document No/Revision	Version 1.0
ClinicalTrials.gov Identification	NCT05093868
Objectives	To correlate electrogram morphology of atrial fibrillation measured by a high-density regional mapping to low density global electrographic flow mapping generated by the Ablamap® software
Procedure	10 subjects with persistent atrial fibrillation
Test Devices	Ablamap® Software v.9.0.2 (With Abbott FIRMap Catheter)
Study Design	Prospective, observational, single center pilot trial
Clinical Site	Herz-und Diabeteszentrum NRW, Ruhr-Universitat Bochum, Bad Oeynhausen, Germany
Study Endpoint	Successful acquisition of global EGF maps from each of the right and left atrial chambers, and simultaneous high density electrogram acquisitions from at least 3 sites in each chamber.
Primary Outcome	Descriptive correlation of electrogram patterns using traditional high density regional mapping versus low density global EGF mapping using a novel mapping software.

2.0 BACKGROUND

2.1 Mapping and ablation of persistent atrial fibrillation

It is hypothesized that initiation and propagation of atrial fibrillation (AF) is dependent, at least in part, on rapid atrial stimulation from focal sources. It is debated whether the mechanism of arrhythmogenesis at these foci is abnormal automaticity, triggered activity, or reentry. However, after activation emerges from these “driver” sites, fibrillatory conduction ensues resulting in the disorganized conduction pattern of AF.^{1,2}

Conventional mapping systems can either achieve high spatial resolution by sequential tachycardia beats following a fixed intra-atrial activation pattern (as in macroreentrant atrial flutter), or high temporal resolution with very low spatial resolution achieved through multielectrode basket catheters. Activation mapping in AF with commercially available mapping systems has been unsuccessful in identifying driver sites because atrial activation patterns change on a beat-to-beat basis precluding the use of sequential mapping approaches, and real-time mapping with basket electrodes lacks sufficient resolution to delineate the complex patterns of conduction.^{2,3}

2.2 Ablamap® mapping system

Electrographic Flow (EGF) mapping (Ablamap®, Ablacon, Inc, Wheat Ridge, CO) is a unique method to assess dominant patterns of intra-atrial conduction during ongoing atrial fibrillation and has been previously described.⁴⁻⁶ EGF mapping reconstructs global atrial wavefront propagation in near real-time. Recordings from a multielectrode basket catheter are analyzed for electrical wavefront activation over sequential 2-second segments during a 60 second acquisition period. Patterns of reproducible wavefront activation are used to identify driver sources for AF. Multiple sources are often identified in patients with persistent AF.⁷ It is anticipated that substrate modification of these source regions will eliminate the AF drivers and result in a favorable response to catheter ablation as shown in a previously published retrospective analysis.⁸

[figure not shown]

Figure 1: FIRMap basket mapping catheter (left) captures 64 unipolar electrograms (center). After undergoing biharmonic spline interpolation based on Green's function, the moving image is produced (right).

[figure not shown]

Figure 2: The transformed data are divided into 2 second segments and activation vectors are produced (center). Multiple segments are compared, and dominant activation wavefronts (vector flows) are identified (right).

[figure not shown]

Figure 3: The summated over multiple segments and a composite map identifying reproducible sources (red dots, right) are identified. It is hypothesized that these source areas are the locations of microreentry, triggered or rotational activity that account for the persisting activation and re-activation of atrial fibrillation wavefronts. Flow consistency of the wavefront activation is weighted on a color scale of blue (low consistency) to maroon (high consistency).

2.3 Electrographic Flow Consistency

In addition to the identification of AF driving sources, EGF mapping allows for the quantification of local and global electrographic flow consistency (EGFC), which measures the overall magnitude and temporal consistency of wavefront patterns.⁹ Regions of low EGFC are therefore associated with areas of chaotic or slowed conduction and conduction block.

In the context of AF, a well-established correlation exists between bipolar low voltage areas detected on high density electroanatomic mapping and the presence of scar tissue as revealed by late gadolinium-enhanced cardiac magnetic resonance imaging, a surrogate marker for atrial fibrosis. Areas of atrial scar, as identified from bipolar voltage maps, have also been associated with worse outcomes, and larger low voltage areas obtained during SR mapping have been associated with the presence and progression of AF.^{10,11} This study aims to extend this understanding by investigating the correlation between bipolar voltage maps and EGFC in multiple rhythms to correlate areas of delayed versus healthy conduction.

2.4 Preliminary Clinical Data of Ablamap®

The FLOW-AF study (NCT 04473963) was a prospective, randomized controlled multi-center study to evaluate the reliability of the CE-marked EGF algorithm technology (Ablamap®, Ablacon, Inc, Wheat Ridge, CO), which identified AF sources and guided ablation therapy in patients with persistent atrial fibrillation. In total, 85 patients with persistent or long-standing persistent AF indicated for redo ablation were enrolled in the FLOW-AF study. In this population, EGF

mapping identified AF sources for ablation in 60% of the patients. Source elimination by means of radiofrequency ablation was achieved in 95.0% (19/20 patients). AF-free survival at 12-months was improved among patients randomized to PVI+EGF-guided source ablation (68%) versus PVI-alone (17%; $p = 0.042$); freedom from AF/AT/AFL at 12-months was 51% versus 14% ($p=0.103$), respectively. Freedom from adverse safety events was 97.2%. Two adverse safety events occurred (decompensated heart failure and arteriovenous fistula), both of which were adjudicated by an independent Clinical Events Committee as related to the procedure but not related to EGF mapping/ablation. EGF-guided ablation of AF sources seems to be an efficacious adjunct to PVI in non-paroxysmal AF patients undergoing redo-ablation. Publication of the FLOW-AF trial is expected in the first quarter of 2024.

In addition, several sites in the EU have been and continue to perform commercial cases using the CE-marked Ablamap® software, and over 172 additional patients have been treated with ablation using EGF-guidance outside of the FLOW-AF randomized clinical trial.

3.0 STUDY DESIGN

3.1 Objectives

To identify driver sources in subjects with ongoing AF using EGF mapping and describe the activation patterns observed from concomitant high density (HD) mapping of those regions.

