3.2 Study Endpoint

Successful acquisition of global EGF maps from each of the right and left atrial chambers and simultaneous high density electrogram acquisitions from at least 3 sites in each chamber.

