3.4 Study Population

Subjects with persistent or longstanding persistent AF that are scheduled for elective catheter ablation of AF (De Novo and Redo).

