4.2 Study Procedure

4.2.1 Catheter Ablation Procedure

- During the study, subjects with PeAF or long-standing PeAF are prospectively enrolled at the Heart and Diabetes Center NRW in Bad Oeynhausen, Germany.
- All subjects should be able to provide written informed consent and should be at least 18 years of age.
- All procedures are performed under sedation after obtaining informed consent.
- All subjects included in this analysis will undergo 3-dimensional electroanatomic mapping with an Ensite mapping system (Abbott, Abbott Park, IL) and Ablamap®.

- Pulmonary vein isolation (PVI) ablation or PVI touch-up should be performed according to standard hospital ablation procedures, using an irrigated tip radiofrequency ablation catheter.
- Ablation catheter power and temperature settings are at the operator's discretion.
- Intravenous heparin should be administered for systemic anticoagulation to maintain an activated clotting time (ACT) > 300 seconds prior to insertion of the 64-pole basket mapping catheter.

4.2.2 *High-Density Voltage Mapping and EGF Mapping*

- All subjects should first undergo high-density voltage mapping using the 16-pole grid mapping catheter (HD-Grid, Abbott, Abbott Park, IL) followed by baseline EGF mapping in their presenting rhythm: AF or SR.
- PVI is then performed in standard fashion at the physician's discretion.
- For any ablation of PVs, confirmation of PVI (entrance or exit block) should be performed after a mandatory minimum 20-minute wait after the last RF application. PV reconnections should be ablated when necessary.
- By necessity, the workflow will vary depending on the subject's presenting rhythm (SR or AF).
 - o If subjects present in SR, they undergo both EGF mapping and high-density bipolar voltage mapping in SR first, followed by PVI. Post-PVI, AF should be induced and EGF mapping and high-density bipolar voltage mapping in AF is then be performed. Cardioversion back to SR should be performed at the end of the procedure.
 - o If subjects present in AF, they undergo EGF mapping and high-density bipolar voltage mapping in AF first, followed by PVI. Post-PVI, if the subject remained in AF, cardioversion should be performed followed by EGF mapping and high-density bipolar voltage mapping in SR.

4.2.3 *EGF Mapping*

- EGF mapping should be performed both pre- and post-PVI using the Ablamap® software (Ablacon, Inc., Wheat Ridge, CO).

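### Objective 3.1 describes HD patterns at EGF sources only, and no source versus non-source comparison or source-level denominator is pre-specified

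*Combined protocol and SAP*

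**What the plan says.** - **Objective, section 3.1.** Driver sources are to be identified by EGF mapping in ongoing AF. The study will then "describe the activation patterns observed from concomitant high density (HD) mapping of those regions", the regions being those sources.
- **Objective and primary outcome, section 1.0.** The summary objective is wider: "To correlate electrogram morphology of atrial fibrillation measured by a high-density regional mapping to low density global electrographic flow mapping". The primary outcome is "Descriptive correlation of electrogram patterns using traditional high density regional mapping versus low density global EGF mapping using a novel mapping software". Neither mentions sources.
- **Endpoint, section 3.2.** It asks for EGF maps of both atria and "simultaneous high density electrogram acquisitions from at least 3 sites in each chamber". No source has to be found, and no HD site has to lie on or off one.
- **Analysis, sections 5.1 to 5.3.** Section 5.1 averages EGFC over the basket electrodes and then over positions within an atrium. Section 5.2 compares EGF patterns and EGFC with unipolar and bipolar voltage maps of the same regions. Section 5.3 provides t-tests and chi-squared tests for group comparisons but does not say what the groups are.
- **Mapping order, section 4.2.2.** "All subjects should first undergo high-density voltage mapping using the 16-pole grid mapping catheter", with baseline EGF mapping after it.
- **Earlier yield, section 2.4.** In the sponsor's randomized redo-ablation study, EGF "mapping identified AF sources for ablation in 60% of the patients".
- **Size and population.** Section 1.0 gives "10 subjects with persistent atrial fibrillation". Section 3.4 admits both de novo and redo patients.

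**The concern.** The study title calls this an electrogram validation, and the summary objective is to correlate HD morphology with EGF mapping. Correlating a feature with a label needs the feature observed at both levels of the label. Section 3.1 looks at one level only, the regions that EGF calls sources. Fractionated, rotational or focal-looking electrograms may be just as common elsewhere in the atrium, and a source-only description would not reveal it.

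The endpoint does not close the gap. Any three sites per chamber satisfy it, so a report could give full acquisition success and a list of patterns seen at sources without saying how many subjects had a source. A reader would naturally ask whether those patterns differ from the rest of the atrium, and the plan has no prepared answer. If comparator sites are picked after both maps have been seen, the choice is open to selection.

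**Working it through.** **Is there a planned contrast?** The plan's sample size of 10 comes with no effect size, standard deviation, rate or power, so there is no calculation to reproduce. The main check is textual.

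| Section | Covers | Source versus non-source contrast? |
|---|---|---|
| 1.0 objective and outcome | HD morphology against EGF mapping in general | Not stated |
| 3.1 | HD activation patterns at EGF sources | No; sources only |
| 3.2 | Acquisition at 3 or more sites per chamber | No; sites unrestricted |
| 5.1 | EGFC averaged by position and by atrium | No; no source-level quantity |
| 5.2 | EGF patterns and EGFC against voltage maps | Not stated; no HD activation variable |
| 5.3 | Tests for group comparisons | Groups undefined |

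If all 10 subjects meet the endpoint, there are at least 3 sites × 2 chambers × 10 subjects = 60 HD sites. None of them is required to be a source site or a comparator.

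**How many subjects may have no source?** Let p be the proportion of subjects with at least one source, and treat subjects as independent, so that the number with a source is Binomial(10, p). Section 2.4 gives p = 60%. Applying it here is an assumption, because that population was redo only. A range of 40% to 80% is therefore shown.

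| p | Expected with a source, 10p | Expected without, 10(1 − p) | P(at least one without), 1 − p^10 | P(5 or fewer with a source) |
|---|---|---|---|---|
| 40% | 4 | 6 | more than 99.9% | 83% |
| 60% | 6 | 4 | 1 − 0.0060 = 99.4% | 37% |
| 80% | 8 | 2 | 1 − 0.1074 = 89.3% | 3% |

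At p = 60%, the probability that 4 or fewer subjects have a source is 17%, and the 95% range for the number with a source is 3 to 9.

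**What does a source-only result say?** Suppose 6 subjects contribute one source each and all 6 show a given pattern. The exact 95% lower limit for its frequency at sources is 0.025^(1/6) = 0.54, so the interval is 54% to 100%. Nothing follows about its frequency elsewhere.

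**What would a comparator add at this size?** Take 6 within-subject pairs, one source site and one non-source site each. An exact two-sided sign test gives 2 × 0.5^6 = 0.031 if all 6 differ in the same direction. With 5 of 6 in one direction it gives 2 × (6 + 1)/64 = 0.219. If the pattern is truly present at 80% of source sites and 20% of non-source sites, taken as independent, power is about 7% with 6 pairs and 56% with 10. At 90% and 10% it is 28% and 93%. With about 6 pairs the contrast is useful as description, not as a test.

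**The case against.** The strongest reply is that section 3.1 is not the whole plan. HD voltage mapping precedes baseline EGF mapping, so it is not aimed at sources. The endpoint sites are unrestricted, and the summary objective is a general correlation. Section 5.2, read with the aim in section 2.3, already contrasts tissue of low and high flow consistency against voltage. The study calls itself a descriptive observational pilot and nowhere promises to show that a pattern is characteristic of sources.

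Much of this stands, and it rules out three stronger readings:

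- A reader might infer that the study can never distinguish source from non-source tissue, or that no comparator sites will exist. The documents point the other way: off-source HD data will probably be recorded.
- A reader might infer that source-free subjects contribute nothing to 3.1. They inform its first half, the identification of sources, and also the comparison in 5.2.
- A reader might infer that source versus non-source is the only way for HD data to bear on EGF mapping. The voltage and EGFC comparison is another, though it does not examine the source label.

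The objection does not supply the missing analysis. The HD mapping placed first is voltage mapping, whereas 3.1 concerns activation patterns in ongoing AF. Subjects who present in SR are mapped in SR first, and section 4.2.4 lets maps be omitted. Incidental off-source recordings become a comparison only if the plan says how they will be labelled and tabulated. The descriptive status of the study is no obstacle, since the remedy is descriptive too.

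**Conclusion.** The point holds as a gap in pre-specification. The description in 3.1 covers source regions only, and the plan sets no source versus non-source comparison and no source-level denominator. That description alone therefore cannot support a statement that any pattern is characteristic of a source.

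The endpoint can be met without a source. About 4 of 10 subjects would be in that position at the 60% yield, and about 2 to 6 of 10 at assumed yields of 80% to 40%. At least one such subject is likely throughout that range (89% or more). These counts rest on carrying a redo-population yield over to a mixed population and on independence between subjects. They measure the mismatch between endpoint and objective. The missing comparison follows from the text whatever the yield.

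This is a worthwhile change to what the study can conclude, not a fatal flaw.

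**What to change.** **In sections 3.1 and 5.2:**
- At analysis, label each HD site recorded in AF as inside or outside an EGF-identified source region of the same chamber and rhythm. Write down the rule for inside and outside before it is applied; the documents give none.
- Describe the same HD features at both kinds of site, preferably read without knowledge of the EGF label.
- Tabulate the results within subject, with intervals and no hypothesis test. Source-free subjects contribute non-source sites.

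**Beside the acquisition endpoint:** report the number of subjects and of chambers with at least one source, as the denominator for the source description.

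**Cost:** some extra analysis work and revised wording. No added patients or procedures are needed, and the mapping order and site minimum do not change, because the labels go on recordings already planned. The limit is size: with about 6 expected within-subject pairs, and fewer if maps are omitted or no HD site falls on a source, the contrast stays descriptive.

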3.2 Study Endpoint

Successful acquisition of global EGF maps from each of the right and left atrial chambers and simultaneous high density electrogram acquisitions from at least 3 sites in each chamber.

3.3 Design

Prospective, observational, single center pilot trial.

3.4 Study Population

Subjects with persistent or longstanding persistent AF that are scheduled for elective catheter ablation of AF (De Novo and Redo).

3.5 Subject Selection

3.5.1 Subject Identification

All subjects who are scheduled for catheter ablation of AF, including those with prior history of AF catheter ablation, were considered. Screening was performed by physician staff at the time of procedure scheduling.

3.5.2 Inclusion Criteria

Subjects will be eligible to participate if the following criteria are met:

- Scheduled to undergo elective catheter ablation of AF
- History of persistent or longstanding persistent AF
- Able to provide written informed consent prior to the procedure
- Age ≥ 18 years

3.5.3 Exclusion Criteria

Subjects will not be eligible to participate if any of the following criteria are met:

- Presence of a permanent pacemaker or other transvenous pacing/defibrillation leads
- Presence of a prosthetic mitral heart valve
- Known reversible causes of AF
- Any cerebral ischemic event (strokes or transient ischemic attacks) which occurred during the 6-month interval preceding the consent date
- History of thromboembolic event within the past 6 months or evidence of intracardiac thrombus at the time of the procedure
- Unable to provide own informed consent

3.5.4 Informed Consent

- Written informed consent was obtained from the subject by the research coordinator or investigator within 30 days of the procedure.

4.0 STUDY METHODS

4.1 Baseline Data

Subjects will undergo baseline evaluation in accordance with hospital's standards.

4.2 Study Procedure

4.2.1 Catheter Ablation Procedure

- During the study, subjects with PeAF or long-standing PeAF are prospectively enrolled at the Heart and Diabetes Center NRW in Bad Oeynhausen, Germany.
- All subjects should be able to provide written informed consent and should be at least 18 years of age.
- All procedures are performed under sedation after obtaining informed consent.
- All subjects included in this analysis will undergo 3-dimensional electroanatomic mapping with an Ensite mapping system (Abbott, Abbott Park, IL) and Ablamap®.

- Pulmonary vein isolation (PVI) ablation or PVI touch-up should be performed according to standard hospital ablation procedures, using an irrigated tip radiofrequency ablation catheter.
- Ablation catheter power and temperature settings are at the operator's discretion.
- Intravenous heparin should be administered for systemic anticoagulation to maintain an activated clotting time (ACT) > 300 seconds prior to insertion of the 64-pole basket mapping catheter.

4.2.2 *High-Density Voltage Mapping and EGF Mapping*

- All subjects should first undergo high-density voltage mapping using the 16-pole grid mapping catheter (HD-Grid, Abbott, Abbott Park, IL) followed by baseline EGF mapping in their presenting rhythm: AF or SR.
- PVI is then performed in standard fashion at the physician's discretion.
- For any ablation of PVs, confirmation of PVI (entrance or exit block) should be performed after a mandatory minimum 20-minute wait after the last RF application. PV reconnections should be ablated when necessary.
- By necessity, the workflow will vary depending on the subject's presenting rhythm (SR or AF).
 - o If subjects present in SR, they undergo both EGF mapping and high-density bipolar voltage mapping in SR first, followed by PVI. Post-PVI, AF should be induced and EGF mapping and high-density bipolar voltage mapping in AF is then be performed. Cardioversion back to SR should be performed at the end of the procedure.
 - o If subjects present in AF, they undergo EGF mapping and high-density bipolar voltage mapping in AF first, followed by PVI. Post-PVI, if the subject remained in AF, cardioversion should be performed followed by EGF mapping and high-density bipolar voltage mapping in SR.

4.2.3 *EGF Mapping*

- EGF mapping should be performed both pre- and post-PVI using the Ablamap® software (Ablacon, Inc., Wheat Ridge, CO).
- Unipolar electrograms (EGMs) are recorded using a commercially available 64-electrode basket mapping catheter (FIRMap™, Abbott Laboratories, Abbott Park, IL) connected to a proprietary, CE-marked recording system (EP Map, Herdecke, Germany).
- EGF mapping is performed by obtaining 1-minute recordings from the 64-pole basket catheter placed in multiple standardized positions within each atrium.
- In the LA, there are typically 2 standardized basket positions: 1) posterosuperior LA with the dome of the basket aiming toward the left

PVs and LA appendage (LAA); 2) lateral LA with basket dome pointing toward LAA and the mitral valve.

- In the right atrium (RA), there are typically 3 standardized basket positions: 1) superior vena cava (SVC)/RA junction with basket position halfway into the SVC; 2) central RA with basket dome pointing to SVC with vertical catheter shaft orientation and basket expanded to fill RA; 3) anterolateral RA with basket dome pointing to RA appendage and tricuspid valve and catheter deflected anterior and lateral from SVC.
- If additional rhythm changes occurred spontaneously, EGF mapping should be conducted in the new rhythm without requiring accompanying voltage maps.

4.2.4 *Procedure Completion*

- Due to time considerations and other practical considerations, voltage maps and EGF maps can be omitted from the protocol at the physician's discretion.
- Adjunctive ablations can be performed at physician's discretion, after all mapping is completed. This includes EGF-identified source ablations.
- Before concluding the procedure, any subjects who are in AF are cardioverted to SR.
- At the end of the procedure, heparin is discontinued. Catheters and sheaths are removed, and hemostasis is achieved per standard protocol.
- The de-identified raw electrogram signal data should be downloaded onto portable media. These anonymized data should be securely transmitted electronically to the technical staff at Ablacon, Inc. for analysis.

